6.10 Prohibited Concomitant Medications whilst receiving Pembrolizumab

Patients are prohibited from receiving the following therapies during the Screening and Treatment period (including retreatment for post-complete response relapse) of this trial:

- Antineoplastic systemic chemotherapy or biological therapy;
- Immunotherapy not specified in this protocol;
- Chemotherapy not specified in this protocol;
- Investigational agents other than bemcentinib and pembrolizumab;
- Radiation therapy:
 - Note: Radiation therapy to a symptomatic solitary lesion or to the brain may be considered on an exceptional case by case basis after consultation with Sponsor. The patient must have clear measurable disease outside the radiated field. Administration of palliative radiation therapy will be considered clinical progression for the purposes of determining PFS. *Note: Treatment with pembrolizumab and bemcentinib must have been discontinued at least one week prior to radiotherapy and should not be restarted within one week of completing radiotherapy.*
- Live vaccines within 30 days prior to the first dose of trial treatment and while participating in the trial. Examples of live vaccines include, but are not limited to, the following: measles, mumps, rubella, chicken pox, yellow fever, rabies, BCG, and

BerGenBio ASA
[name]
[name]
Norway

typhoid (oral) vaccine. Seasonal influenza vaccines for injection are generally killed virus vaccines and are allowed. However, intranasal influenza vaccines (e.g., Flu - Mist®) are live attenuated vaccines, and are not allowed;

- Systemic glucocorticoids for any purpose other than to modulate symptoms from an event of clinical interest of suspected immunologic etiology. The use of physiologic doses of corticosteroids may be approved after consultation with the Sponsor:
 - Note: Inhaled steroids are allowed for management of asthma.

Patients who, in the assessment by the investigator, require the use of any of the aforementioned treatments for clinical management should be removed from the trial. Patients may receive other medications that the investigator deems to be medically necessary.

The Exclusion Criteria describes other medications that are prohibited in this trial.

There are no prohibited therapies during the Follow Up period once the patient has discontinued both treatments.

6.11 Supportive Care Guidelines and Rescue Medications for Pembrolizumab

Patients should receive appropriate supportive care measures as deemed necessary by the treating investigator. Suggested supportive care measures for the management of AEs with potential immunologic etiology are outlined below. Where appropriate, these guidelines include the use of oral or intravenous treatment with corticosteroids as well as additional anti-inflammatory agents if symptoms do not improve with administration of corticosteroids.

Note that several courses of steroid tapering may be necessary as symptoms may worsen when the steroid dose is decreased. For each disorder, attempts should be made to rule out other causes such as metastatic disease or bacterial or viral infection, which might require additional supportive care. The treatment guidelines are intended to be applied when the investigator determines the events to be related to pembrolizumab.

Note: If after the evaluation the event is determined not to be related, the investigator does not need to follow the treatment guidance (as outlined below). Refer to [Section 6.6](#) for dose modification.

It may be necessary to perform conditional procedures such as bronchoscopy, endoscopy, or skin photography as part of evaluation of the event.

6.12 Infusion Guidelines for Pembrolizumab

Signs and symptoms usually develop during or shortly after drug infusion and generally resolve completely within 24 hours of completion of infusion.

[Table 18](#) shows treatment guidelines for patients who experience an infusion reaction associated with administration of pembrolizumab.

BerGenBio ASA
[name]
[name]
Norway

Table 18: Management of Pembrolizumab-associated Infusion-related Reactions

NCI CTCAE (v 5.0) Grade	Treatment	Premedication at subsequent dosing
Grade 1 Mild reaction; infusion interruption not indicated; intervention not indicated	Increase monitoring of vital signs as medically indicated until the subject is deemed medically stable in the opinion of the investigator.	None
Grade 2 Requires infusion interruption but responds promptly to symptomatic treatment (e.g., antihistamines, NSAIDS, narcotics, IV fluids); prophylactic medications indicated for <=24 hrs	Stop Infusion and monitor symptoms. Additional appropriate medical therapy may include but is not limited to: IV fluids Antihistamines NSAIDS Acetaminophen Narcotics Increase monitoring of vital signs as medically indicated until the subject is deemed medically stable in the opinion of the investigator. If symptoms resolve within one hour of stopping drug infusion, the infusion may be restarted at 50% of the original infusion rate (e.g., from 100 mL/hr to 50 mL/hr). Otherwise, dosing will be held until symptoms resolve and the subject should be premedicated for the next scheduled dose. Subjects who develop Grade 2 toxicity despite adequate premedication should be permanently discontinued from further trial treatment administration.	Subject may be premedicated 1.5h (\pm 30 minutes) prior to infusion of pembrolizumab (MK-3475) with: Diphenhydramine 50 mg po (or equivalent dose of antihistamine). Acetaminophen 500-1000 mg po (or equivalent dose of antipyretic).

BerGenBio ASA
[name]
[name]
Norway

NCI CTCAE (v 5.0) Grade	Treatment	Premedication at subsequent dosing
Grades 3 or 4 Grade 3: Prolonged (i.e., not rapidly responsive to symptomatic medication and/or brief interruption of infusion); recurrence of symptoms following initial improvement; hospitalization indicated for other clinical sequelae (e.g., renal impairment, pulmonary infiltrates) Grade 4: Life-threatening; pressor or ventilatory support indicated	Stop Infusion. Additional appropriate medical therapy may include but is not limited to: IV fluids Antihistamines NSAIDs Acetaminophen Narcotics Oxygen Pressors Corticosteroids Epinephrine Increase monitoring of vital signs as medically indicated until the subject is deemed medically stable in the opinion of the investigator. Hospitalization may be indicated. Subject is permanently discontinued from further trial treatment administration.	No subsequent dosing

Appropriate resuscitation equipment should be available in the room and a physician readily available during the period of drug administration.

6.13 Diet, Activity and Other Considerations

6.13.1 Diet

Patients should maintain a normal diet unless modifications are required to manage an AE such as diarrhea, nausea or vomiting.

6.14 Contraception

Pembrolizumab and bemcentinib may have adverse effects on a fetus in utero. Furthermore, it is not known if pembrolizumab has transient AEs on the composition of sperm. For this trial, male patients will be considered to be of non-reproductive potential if they have azoospermia (whether due to having had a vasectomy or due to an underlying medical condition).

Female patients will be considered of non-reproductive potential if they are either:

- postmenopausal (defined as at least 12 months with no menses without an alternative medical cause; in women <45 years of age a high FSH level in the postmenopausal range may be used to confirm a post-menopausal state in women not using hormonal contraception or hormonal replacement therapy. In the absence of 12 months of amenorrhea, a single FSH measurement is insufficient.);

OR

- have had a hysterectomy and/or bilateral oophorectomy, bilateral salpingectomy or bilateral tubal ligation/occlusion, at least 6 weeks prior to screening;

OR

- has a congenital or acquired condition that prevents childbearing.

BerGenBio ASA
[name]
[name]
Norway

Female and male patients of reproductive potential must agree to use highly effective methods of contraception while receiving study drug and for 120 days after the last dose of study drug by complying with one of the following highly effective methods[‡]:

- Combined (estrogen and progestogen containing) hormonal contraception associated with inhibition of ovulation:
 - Oral
 - Intravaginal
 - Transdermal
- Progestogen-only hormonal contraception associated with inhibition of ovulation:
 - Oral
 - Injectable
 - implantable
- intrauterine device (IUD);
- intrauterine hormone-releasing system (IUS);
- bilateral tubal occlusion;
- vasectomized partner;
- practice abstinence from heterosexual activity[†]

[†]Abstinence (relative to heterosexual activity) can be used as the sole method of contraception if it is consistently employed as the patient's preferred and usual lifestyle and if considered acceptable by local regulatory agencies and Institutional Review Board (IRB)/Institutional Ethics Committee (IECs). Periodic abstinence e.g., calendar, ovulation, sympto-thermal, post-ovulation methods, etc. and withdrawal are not acceptable methods of contraception.

[‡]If a contraceptive method listed above is restricted by local regulations/guidelines, then it does not qualify as an acceptable method of contraception for patients participating at sites in this country/region.

Patients should be informed that taking the study medication may involve unknown risks to the fetus (unborn baby) if pregnancy were to occur during the study. In order to participate in the study, patients of childbearing potential must adhere to the contraception requirement (described above) from the day of study medication initiation (or 14 days prior to the initiation of study medication for oral contraception) throughout the study period up to 120 days after the last dose of trial therapy. If there is any question that a patient of childbearing potential will not reliably comply with the requirements for contraception, that patient should not be entered into the study.

BerGenBio ASA
[name]
[name]
Norway

6.14.1 Use in pregnancy

If a patient inadvertently becomes pregnant while on treatment with study medication, the patient will immediately be removed from the study. The site will contact the patient at least monthly and document the patient's status until the pregnancy has been completed or terminated. The outcome of the pregnancy will be reported to the Sponsor without delay and within 24 hours if the outcome is a serious adverse experience e.g., death, abortion, congenital anomaly, or other disabling or life-threatening complication to the mother or new-born. The study Investigator will make every effort to obtain permission to follow the outcome of the pregnancy and report the condition of the fetus or new-born to the Sponsor.

6.14.2 Use in nursing women

It is unknown whether pembrolizumab is excreted in human milk. Since many drugs are excreted in human milk, and because of the potential for serious ARs in the nursing infant, patients who are breast-feeding are not eligible for enrolment.

BerGenBio ASA
[name]
[name]
Norway

7 ADVERSE EVENTS AND REPORTING REQUIREMENTS

7.1 Assessment of Safety

Progression of the cancer under study is not considered an adverse event unless it is considered to be drug-related by the investigator.

All AEs that occur after the consent form is signed but before treatment allocation must be reported by the investigator if they cause the subject to be excluded from the trial or are the result of a protocol-specified intervention, including but not limited to washout or discontinuation of usual therapy, diet, placebo treatment or a procedure.

From the time of treatment allocation through 30 days following cessation of treatment, all AEs must be reported by the investigator. Such events will be recorded at each examination on the Adverse Event case report forms/worksheets.

The reporting timeframe for AEs meeting any serious criteria is described in [Section 7.4.3](#). The investigator will make every attempt to follow all subjects with non-serious AEs for outcome. **From the time of treatment allocation through 90 days following cessation of treatment, all SAEs (including serious events of special interest) must be reported by the investigator.** Where a patient has initiated a new cancer treatment, the time period is 30 days after cessation of treatment. See [Section 7.4.3.1](#) and [Section 7.4.3.2](#).

The reporting timeframe for a new pregnancy is described in [Section 7.5](#).

7.2 Adverse Event Definition

An AE is any untoward medical occurrence in a patient or clinical study subject administered a pharmaceutical product and which does not necessarily have a causal relationship with the product. An AE can therefore be any unfavorable or unintended sign, symptom or disease temporally associated with the use of the IMP whether or not considered related to the IMP. This includes any occurrence that is new, an exacerbation of an existing disease (a worsening of the character, frequency or severity of a known condition) or abnormal results of diagnostic procedures, including clinically significant laboratory test abnormalities.

Suggested criteria for the assessment of clinical significance for laboratory abnormalities are as follows.

The laboratory abnormality:

- is clearly consistent with the pattern of the patient's underlying disease or disease progression;
- is accompanied by clinical symptoms;
- requires study drug dose modification or interruption or permanent discontinuation of study treatment;
- requires more frequent follow-up assessments, further diagnostic investigation, etc.;
- requires a change in concomitant medication, therapy, or treatment.

If the clinically significant laboratory abnormality is a sign of a disease or syndrome (e.g., alkaline phosphatase and bilirubin 5X ULN associated with cholecystitis), only the diagnosis (e.g., cholecystitis) needs to be recorded on the AE CRF. If the clinically significant laboratory

BerGenBio ASA
[name]
[name]
Norway

abnormality is not a sign of a disease or syndrome, the abnormality itself should be recorded as an AE or SAE on the CRF. If the laboratory abnormality can be characterized by a precise clinical term, the clinical term should be recorded as the AE or SAE. For example, an elevated serum potassium level of 7.0 mEq/L should be recorded as “hyperkalemia.” Observations of the same clinically significant laboratory abnormality from visit to visit should not be repeatedly recorded as AEs or SAEs on the CRF, unless their severity, seriousness, or etiology changes.

For all AEs, a diagnosis should be recorded on the CRF rather than individual signs and symptoms (e.g., record only liver failure or hepatitis rather than jaundice, asterixis, and elevated transaminases) wherever possible. However, if a constellation of signs and/or symptoms cannot be medically characterized as a single syndrome at the time of reporting, each individual sign and/or symptom should be recorded as an AE or SAE on the CRF. If a diagnosis is subsequently established, the reported event term should be updated to reflect the medical diagnosis.

Note that AEs occurring secondary to an initiating event that are separated in time or medically significant should be recorded as independent events on the CRF. For example, if a severe gastrointestinal hemorrhage leads to a renal failure, both events should be recorded separately on the CRF.

A pre-existing medical condition which is present at the start of the study and described in the Medical History CRF, should only be recorded as an AE or SAE if the frequency, severity, or character of the condition worsens during the study. When recording such events on the AE CRF, it is important to convey the concept that the pre-existing condition has changed by including applicable descriptors (e.g., “more frequent headaches”).

Surgical procedures or other therapeutic interventions themselves are not AEs, but the condition for which the surgery/intervention is required is an AE and should be documented accordingly.

Planned surgical measures and the condition(s) leading to these measures are not AEs, if the condition(s) was (were) known before the period of observation and did not worsen during study. In the latter case, the condition should be reported as medical history.

During clinical trials, AEs can be spontaneously reported or elicited during open-ended questioning, examination, or evaluation of a patient. To prevent reporting bias, patients should not be questioned regarding the specific occurrence of one or more AEs.

Symptoms and signs of exacerbation or worsening of the patient’s primary disease will not be captured as AEs. Progression of the disease under study (i.e., NSCLC) will not be captured as an AE unless it is considered to be drug-related by the Investigator.

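### In Section 7.2, the first criterion for a clinically significant laboratory abnormality points the opposite way from the rule that worsening of the cancer is not recorded as an adverse event

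*Combined protocol and SAP*

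**What the plan says.** Section 7.2 extends the AE definition to "abnormal results of diagnostic procedures, including clinically significant laboratory test abnormalities". It then introduces a list: "Suggested criteria for the assessment of clinical significance for laboratory abnormalities are as follows". The first of five bullets is that the abnormality "is clearly consistent with the pattern of the patient's underlying disease or disease progression". The other four are accompanying symptoms, a change to study drug ("requires study drug dose modification or interruption or permanent discontinuation of study treatment"), more follow-up or investigation, and a change in other treatment.

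Two recording rules follow. If the abnormality is a sign of a disease or syndrome, only the diagnosis goes on the AE form. If the "abnormality is not a sign of a disease or syndrome, the abnormality itself should be recorded as an AE or SAE on the CRF".

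Section 5.3.6 adds that a clinically significant safety laboratory finding after dosing will be recorded as an AE where it is a change from baseline. It makes no exception for progression.

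Section 7.2 closes with: "Symptoms and signs of exacerbation or worsening of the patient’s primary disease will not be captured as AEs". The next sentence is: "Progression of the disease under study (i.e., NSCLC) will not be captured as an AE unless it is considered to be drug-related", with the Investigator making that judgment. Section 7.1 gives the same rule for progression.

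**The concern.** The list is the protocol's only guidance on when a laboratory value is clinically significant, and significance is what makes a value an AE. Consistency with the cancer or its progression is listed as a reason for significance. The closing paragraph of the same section treats the same feature as a reason not to record. An investigator who sees a laboratory change explained by growing metastases can find support in the text for either action.

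At stake is the consistency of AE and SAE counts. The number and frequency of AEs is a secondary endpoint (Section 2). The study plans up to about 20 sites, uses local laboratories, and leaves the judgment to each investigator. It has no control group, so disease-driven events recorded at some sites and not at others are not offset by a comparison. Section 8.12.1.1 tabulates AEs by preferred term, by grade, and for Grade 3 and higher, and these all-cause tables would carry the inconsistency.

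**Working it through.** No arithmetic applies. The check is to follow one case through the text: a post-dose laboratory abnormality, changed from baseline, clearly consistent with NSCLC progression, and not considered drug-related.

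1. **Direction of the list.** The lead-in offers criteria for significance. Symptoms, study drug changes, further follow-up and treatment changes all argue for significance, so this is not a list of exclusions. The first bullet, read with its neighbours, also argues for significance.
2. **Outcome under the list.** The case meets the first bullet. If one bullet is enough, which the text does not say, the value is clinically significant. It is then an AE under the definition in Section 7.2, and Section 5.3.6 says it will be recorded.
3. **Outcome under the exclusion.** The same value is a sign of worsening primary disease, so the closing paragraph of Section 7.2 says it is not captured. If it is regarded as progression itself, Sections 7.1 and 7.2 exclude it because it is not considered drug-related.
4. **Outcome under the recording rules.** The value is a sign of a disease, so the instruction to record the abnormality itself does not apply. Only the diagnosis is recorded, and here that is NSCLC progression. The instruction puts the diagnosis on the AE form; the closing paragraph then keeps progression off it. A reader who applies both reaches exclusion. A reader who stops at the list or at Section 5.3.6 does not.
5. **A smaller mismatch.** The sentence on signs and symptoms of worsening has no exception. The sentence on progression excepts drug-related cases. Corrected text has to say which applies to laboratory values.

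Steps 2 and 3 give opposite answers for the same value. Step 4 narrows the conflict but does not remove it.

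**The case against.** The strongest reply is that the two texts do not carry equal weight. The criteria are only suggested, and nothing says a single bullet suffices. The exclusion is categorical, specific to the study disease, and stated in both 7.1 and 7.2. With the diagnosis-only rule, a careful reader would usually leave a progression-driven value unrecorded. This stands, and it limits the effect. It does not settle the matter: Section 5.3.6 makes recording of clinically significant findings an instruction, has no progression exception, and depends on this list for the meaning of significance. Underlying disease might also be read as a comorbidity, but the bullet goes on to name disease progression, which in this trial naturally includes the cancer.

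Three stronger readings are tempting and not supported.

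- A reader might infer that every progression-driven value must be entered as an AE in its own right. That instruction is limited to abnormalities that are not a sign of a disease or syndrome.
- A reader might infer that the liver safety signal is compromised, because raised ALT/AST is named as an overlapping toxicity. The documents do not show this. Section 8.12.1.2 grades laboratory values by CTCAE where a grade exists, lists them all and gives shift tables. The ALT/AST dose-modification rules work on grade. The combined liver-test event of clinical interest in Section 7.4.3.2 is defined by thresholds and reported whether or not related. AEs are also tabulated by relationship to both drugs.
- A reader might infer that the sponsor meant the opposite and dropped a 'not'. That is plausible, but the documents do not say so.

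**Conclusion.** The inconsistency is real and sits in operative text. The first criterion in Section 7.2 makes consistency with the disease or its progression a mark of clinical significance, while Sections 7.1 and 7.2 exclude the same events unless drug-related. The likely consequence is uneven recording of progression-driven laboratory AEs between sites.

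Its size cannot be estimated from the documents. A reader might try: if 60% to 80% of 106 patients progressed while AEs were collected, and 10% to 30% of those had a progression-type laboratory change, the range would be 106 × 0.60 × 0.10 = 6.4 to 106 × 0.80 × 0.30 = 25.4 patients. Those rates have no source in the documents. The base of 106 is the planned maximum evaluable for efficacy, not the safety set. The calculation also assumes that the diagnosis-only rule never applies. It should not be used as an estimate.

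The response rate analysis, sample size and error rates do not use AE counts and are unaffected, as are the laboratory tables. The conclusion assumes that some investigators would treat one bullet as enough, which the text permits but does not state. The correction is worth making because it is cheap and makes a secondary-endpoint count mean the same thing at every site.

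**What to change.** In Section 7.2, remove the first bullet as a stand-alone criterion and add after the list: *A laboratory abnormality clearly consistent with NSCLC or its progression is not recorded as an AE unless the Investigator considers it drug-related (Section 7.1).* State that any one of the remaining four bullets is enough for clinical significance and that the new sentence takes precedence over them. Without that, a progression-driven value could return through, for example, the bullet on more frequent follow-up. The new sentence also settles that the drug-related exception covers laboratory signs of worsening.

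Cross-refer to this sentence in Section 5.3.6, and state that reporting of the liver-test event of clinical interest in Section 7.4.3.2 is unchanged.

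Two alternatives should be avoided. Simply negating the bullet would, if one bullet suffices, make any trivial out-of-range value not due to cancer clinically significant. Adding a separate exception for abnormalities that lead to a change in study drug would introduce a second exception, when Sections 7.1 and 7.2 allow only drug-relatedness.

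The cost is a short edit to Sections 7.2 and 5.3.6 and to the eCRF completion guidance, and slightly fewer recorded laboratory AEs. The values themselves remain in the laboratory listings, visit summaries and shift tables.
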